### **Duration of Each Local Reaction**

For subjects experiencing any local reactions (or those with a derived reaction as described in [Table 4](#)), the maximum duration (last day of reaction – first day of reaction + 1) will be derived for each study vaccination. Resolution of the event is the last day on which the event is recorded in the e-diary or the date the event ends if it is unresolved during the subject diary-recording period (end date collected on the CRF), unless chronicity is established. If there is no known end date, the duration will be considered unknown and set to “missing.” However, if an event is ongoing at the time of a subsequent vaccination, the end date/day for the ongoing event will be the date/day that the next vaccination is administered, which will be used for the duration computation. Subjects with no reported reaction have no duration.

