7.1.1. Electronic Diary

Subjects will be required to use an e-diary, based on appropriate technology, and will be asked to monitor and record local reactions and systemic events from Day 1 to Day 7, with Day 1 being the day of vaccination, following each vaccination. The e-diary allows recording of these assessments only within a fixed time window, thus providing the accurate representation of the subject's experience at that time. Data on local reactions and systemic events reported on the e-diary will be transferred electronically to a third-party vendor, where they will be available for review by investigators and the Pfizer clinicians at all times via an internet-based portal. E-diary data review is ongoing during subject e-diary data-entry periods (from Day 1 to Day 7, with Day 1 being the day of vaccination) via an internet-based portal.

At intervals agreed to by the vendor and Pfizer, these data will be transferred electronically into Pfizer's database for analysis and reporting. These data do not need to be reported by the investigator in the CRF as AEs.

Investigators (or designee) will be required to review the e-diary data online at frequent intervals as part of the ongoing safety review.

The investigator or designee should obtain stop dates for any ongoing local reactions or systemic events on the last day that the e-diary was completed. The stop dates should be documented in the source documents and the information entered in the CRF.

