**Table 7. Systemic Event Grading Scale**

	Mild (Grade 1)	Moderate (Grade 2)	Severe (Grade 3)	Potentially Life Threatening (Grade 4)
Vomiting	1-2 times in 24 hours	>2 times in 24 hours	Requires IV hydration	Emergency room visit or hospitalization for hypotensive shock
Headache	No interference with activity	Some interference with activity	Significant; prevents daily activity	Emergency room visit or hospitalization for severe headache
Fatigue/ tiredness	No interference with activity	Some interference with activity	Significant; prevents daily activity	Emergency room visit or hospitalization for severe fatigue
New or worsening muscle pain	No interference with activity	Some interference with activity	Significant; prevents daily activity	Emergency room visit or hospitalization for severe new or worsening muscle pain
New or worsening joint pain	No interference with activity	Some interference with activity	Significant; prevents daily activity	Emergency room visit or hospitalization for severe new or worsening joint pain

Abbreviation: IV = intravenous.

For each systemic event, the following variables will be available, similar to local reactions:

1. Each systemic event on **CCI** any day (Day 1 to Day 7) after each vaccination and after any vaccination.
2. Any systemic event (including fever as described in Section 3.5.3.3) on **CCI** any day (Day 1 to Day 7) after each vaccination and after any vaccination.
3. Maximum severity of each systemic event on any day (Day 1 to Day 7) after each vaccination and after any vaccination.
4. Maximum duration of each systemic event after each vaccination.
5. Onset day of each systemic event after each vaccination.
6. Onset day of any systemic event after each vaccination.

The derivation of these variables is similar to the derivation of the variables for local reactions (Section 3.5.3.1).

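### Reactions with no recorded end date are given no duration, and those cut at the next vaccination carry no flag, so the descriptive duration variable can understate the longest reactions

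*SAP*

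**What the plan says.** SAP 3.5.3.1 (Duration of Each Local Reaction) defines duration as last day minus first day plus 1; it "will be derived for each study vaccination". The last day is the final e-diary day with the reaction or, if the reaction outlasts the diary, the end date on the CRF, "unless chronicity is established". Two further rules follow:

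- No end date: "If there is no known end date, the duration will be considered unknown and set to" missing.
- Ongoing at a later vaccination: "the end date/day for the ongoing event will be the date/day that the next vaccination is administered".

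The six derived variables listed for local reactions in SAP 3.5.3.1 include maximum duration. None marks a duration as cut short, censored or ongoing. SAP 3.5.3.2 carries the derivation over to systemic events ("Maximum duration of each systemic event after each vaccination"), and SAP 3.5.3.3 does the same for fever.

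On data collection, Protocol 7.1.1 says that the investigator or designee "should obtain stop dates for any ongoing local reactions or systemic events" on the last diary day and enter them in the CRF. Protocol 7.1.1.2 has persisting local reactions entered in the CRF, and Protocol 6.1.5 has ongoing reactions followed up at Visit 5. Of the transferred e-diary data, Protocol 7.1.1 also says: "These data do not need to be reported by the investigator in the CRF as AEs".

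**The concern.** Whether a duration is missing depends on the duration itself. A reaction that resolves within the diary week supplies its own end date. One that outlasts the diary needs a later contact to supply it, and one that outlasts the final contact may never get one. The values at risk are therefore disproportionately the longest, and the rule discards the minimum duration that is already known.

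The two rules also treat doses differently. The vaccination cut-off needs a later dose, so it cannot operate after Dose 3, or after the last dose in a subject who stops early. At stake is whether a reader can compare duration across doses and groups, and can trust the reported maximum.

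**Working it through.** The plan states no figure on this point to reproduce. The check applies its rule to its own visit windows and then illustrates the effect on assumed data.

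**Inputs from the documents.** Duration = last day − first day + 1, with Day 1 the vaccination day. Visit 2 is 28 to 42 days after Visit 1, Visit 4 is 140 to 168 days after Visit 2, and Visit 5 is 28 to 42 days after Visit 4 (Protocol, Schedule of Activities). A contact g days after a dose falls on Day g + 1, so a reaction with onset on Day d that is still present then has lasted (g + 1) − d + 1 days.

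| Still present at | Day counted from that dose | Onset Day 1 | Onset Day 7 | What the SAP records |
|---|---|---|---|---|
| Visit 2, after Dose 1 | 29 to 43 | 29 to 43 days | 23 to 37 days | that value, unflagged |
| Visit 4, after Dose 2 | 141 to 169 | 141 to 169 days | 135 to 163 days | that value, unflagged |
| Visit 5, after Dose 3 | 29 to 43 | at least 29 to 43 days | at least 23 to 37 days | full duration if a stop date is obtained later; otherwise missing |

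The first and third rows describe the same course observed for the same time. The first rows of the table assume that the next dose is given at the visit.

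**Illustration (all inputs assumed).** Take 100 reactors. Those who resolve in the diary week average 2.62 days with a maximum of 7. Let k of the 100 instead persist to 60 days.

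- True mean = ((100 − k) × 2.62 + k × 60) / 100
- Mean with those k held at 29 days = ((100 − k) × 2.62 + k × 29) / 100. This is both the Dose 1 cut-off at its earliest and the known minimum at the earliest Visit 5.
- Mean with those k set to missing = 2.62

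| k | True mean | Held at 29 days | Set to missing |
|---|---|---|---|
| 1 | 3.19 | 2.88 | 2.62 |
| 2 | 3.77 | 3.15 | 2.62 |
| 5 | 5.49 | 3.94 | 2.62 |

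For k = 1: (99 × 2.62 + 60) / 100 = 3.19 and (99 × 2.62 + 29) / 100 = 2.88. The maximum is 60 days in truth, 29 when held at that value, and 7 when set to missing. At k = 1 the mean moves little, but the maximum changes from at least 29 days to 7. The missing column applies only if no end date is obtained for any of the k.

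**The case against.** The strongest reply is that the protocol already collects what is needed. The stop-date instruction in Protocol 7.1.1 has no cut-off at Visit 5 and does not depend on whether the reaction is an AE. Reactions are followed up at each later visit and, with consent, for 1 month after vaccination is discontinued (Protocol 6.2). A recorded end date keeps the full duration unless a later dose intervenes. This stands and sets the scope of the point.

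A reader might infer that nothing follows diary reactions past Visit 5, so that every reaction ongoing then loses its duration. The documents do not support that. What remains is narrower. The express rules on following events until they resolve or stabilise are in the AE and SAE text (Protocol 8.1.4.1 and 8.1.4.2), a subject lost to follow-up cannot supply a date, and the SAP itself provides for unknown end dates.

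A reader might also infer that reactions cut at the next vaccination vanish. They do not: they stay among the longest values. A cut-off is defensible too, because after another dose a continuing reaction is hard to attribute. The remaining fault is that nothing shows the value was cut.

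Two further replies carry some weight. SAP Table 1 says the duration text was clarified after FDA comments on the data standardization plan, but it does not say that leaving such values unflagged was requested, and a flag preserves the existing derivation. And where the default statistics in SAP 5.2 are used, n would let a reader see missing durations against the number of reactors. It would not identify durations cut at a vaccination.

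**Conclusion.** The point holds as a modest, inexpensive improvement. The rule drops durations when no end date is ever recorded, these are disproportionately the longest reactions, and after a subject's last dose no vaccination date can stand in. Durations cut at a vaccination are understated and appear ended, without a flag. The SAP also gives no value for a reaction whose chronicity is established.

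The effect is confined to a descriptive variable. The reactogenicity results set out in SAP 6.1.2 are presence and maximum severity, which the rule does not touch, and the lot-consistency test is unaffected. No duration table appears in the visible analysis sections, parts of which are redacted.

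The size cannot be fixed from the documents, because they do not say how often stop dates will be missing. Under the assumed illustration, losing 1 to 5 of 100 reactors leaves the mean at 2.62 days against 3.19 to 5.49.

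A reader might link this to the earlier study halted for Grade 3 injection site redness (Protocol 1.2.3.2). That was a finding of severity, with toxoid alone on another schedule. It does not show that duration is a problem here.

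**What to change.** In SAP 3.5.3.1, and by reference in 3.5.3.2 and 3.5.3.3, keep the existing derivation and add the following:

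1. A flag for each duration that was cut at the next vaccination or has no known end date.
2. Where no end date is known, record the minimum duration, up to the last date on which the reaction was documented as ongoing, as a censored value instead of missing.
3. Report counts of cut and ongoing reactions by dose and vaccine group, and show maxima that rest on such values as ≥ x days.
4. State how a reaction with established chronicity is handled in the duration variable.

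The cost is SAP wording, one flag variable and one table row. Means that include censored values are lower bounds and should be labelled so, and reported maxima will look less favourable.

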### **Onset of Each Local Reaction**

The onset day of each local reaction and any local reaction will be derived.

The onset day for each local reaction is the first day the subject reports the local reaction, even if the reaction later becomes more severe. The onset day for “any local reaction” will be the first day of any of the 3 local reactions, regardless of severity. Onset day will be “missing” for subjects without the indicated local reaction.

In summary, the following variables will be derived for local reactions:

1. Each local reaction on [CCI](#) █ any day (Day 1 to Day 7) after each vaccination and after any vaccination.
2. Any local reaction on [CCI](#) █ any day (Day 1 to Day 7) after each vaccination and after any vaccination.
3. Maximum severity of each local reaction on any day (Day 1 to Day 7) after each vaccination and after any vaccination.
4. Maximum duration of each local reaction after each vaccination.
5. Onset day of each local reaction after each vaccination.
6. Onset day of any local reaction after each vaccination.

#### **3.5.3.2. Systemic Event Endpoints**

Systemic events will be reported via e-diary. Subjects will be asked to assess severity of each event as mild, moderate, or severe as specified in [Table 7](#). Only an investigator is able to classify a subject’s systemic event as Grade 4, after physical examination or documentation from another medically qualified source.

**Table 7. Systemic Event Grading Scale**

	Mild (Grade 1)	Moderate (Grade 2)	Severe (Grade 3)	Potentially Life Threatening (Grade 4)
Vomiting	1-2 times in 24 hours	>2 times in 24 hours	Requires IV hydration	Emergency room visit or hospitalization for hypotensive shock
Headache	No interference with activity	Some interference with activity	Significant; prevents daily activity	Emergency room visit or hospitalization for severe headache
Fatigue/ tiredness	No interference with activity	Some interference with activity	Significant; prevents daily activity	Emergency room visit or hospitalization for severe fatigue
New or worsening muscle pain	No interference with activity	Some interference with activity	Significant; prevents daily activity	Emergency room visit or hospitalization for severe new or worsening muscle pain
New or worsening joint pain	No interference with activity	Some interference with activity	Significant; prevents daily activity	Emergency room visit or hospitalization for severe new or worsening joint pain

Abbreviation: IV = intravenous.

For each systemic event, the following variables will be available, similar to local reactions:

1. Each systemic event on **CCI** any day (Day 1 to Day 7) after each vaccination and after any vaccination.
2. Any systemic event (including fever as described in Section 3.5.3.3) on **CCI** any day (Day 1 to Day 7) after each vaccination and after any vaccination.
3. Maximum severity of each systemic event on any day (Day 1 to Day 7) after each vaccination and after any vaccination.
4. Maximum duration of each systemic event after each vaccination.
5. Onset day of each systemic event after each vaccination.
6. Onset day of any systemic event after each vaccination.

The derivation of these variables is similar to the derivation of the variables for local reactions (Section 3.5.3.1).

### 3.5.3.3. Temperature

Oral temperature will be collected in the e-diary, in the evening, daily for 7 days after vaccination. It will also be collected at any time during the e-diary data collection periods that fever is suspected. The highest temperature for each day will be recorded in the e-diary. The protocol defines fever as an oral temperature  $\geq 38.0^{\circ}\text{C}$  ( $\geq 100.4^{\circ}\text{F}$ ). Fever will be categorized as specified in Table 8.

**Table 8. Scale for Fever**

Mild (Grade 1)	38.0-38.4°C (100.4-101.1°F)
Moderate (Grade 2)	38.5-38.9°C (101.2-102.0°F)
Severe (Grade 3)	39.0-40.0°C (102.1-104.0°F)
Potentially life threatening (Grade 4)	>40.0°C (>104.0°F)

Similar to the derivations of systemic events and local reactions, fever will be derived for:

1. Fever on **CCI** any day (Day 1 to Day 7) after each vaccination and after any vaccination.
2. Highest fever (maximum severity) on any day (Day 1 to Day 7) after each vaccination and after any vaccination.
3. Maximum duration of fever after each vaccination.
4. Onset day of fever after each vaccination.

Temperatures <35.0°C and >42.0°C will be excluded from the analysis.

#### **3.5.4. E-Diary Completion**

For any given day, an e-diary will be transmitted and considered as complete if all expected data (the 3 local reactions and the 6 systemic events, including fever) are available. If all data are missing for all items on the e-diary, for all days following vaccination, the e-diary will be considered not transmitted. An e-diary will be considered completed if all expected data for all days are available (ie, not missing) and data are valid. Otherwise, the e-diary will be considered incomplete.

For e-diaries, an indicator variable for the percentage of days without data will be derived as follows:

- = 1, if data have been transmitted and are complete for 7 days (100%)
- = 2, if data have been transmitted and are complete for 6 days ( $\geq 75\%$  to <100%)
- = 3, if data have been transmitted and are complete for 4 or 5 days ( $\geq 50\%$  to <75%)
- = 4, if data have been transmitted and are complete for 2 or 3 days ( $\geq 25\%$  to <50%)
- = 5, if data have been transmitted and are complete for 0 to 1 day (<25%)

#### **4. ANALYSIS SETS**

Data for all subjects will be assessed to determine if subjects meet the criteria for inclusion in each analysis population prior to unblinding and releasing the database, and classifications will be documented per standard operating procedures.

#### **4.1. Evaluable Immunogenicity Population**

The evaluable immunogenicity (EI) population will be the primary population for the immunogenicity analyses. The EI population will consist of all study subjects who:

- Have been enrolled in the study and receive all 3 doses of investigational product to which they were randomized,
- Have blood drawn for assay testing within 23 to 47 days after Visit 4,
- Have valid and determinate assay results for either toxin A or toxin B for the specified analysis, and
- Have no major protocol deviations

#### **4.2. Modified Intent-to-Treat Population**

The modified intent-to-treat (mITT) population will include all randomized subjects who have received at least 1 dose of the investigational product and have at least 1 valid and determinate assay result for either toxin A or toxin B for the specified analysis.

Immunogenicity analyses using the mITT population will be conducted only if the mITT population size exceeds the size of the EI population by  $>5\%$ . If the difference between the sizes of the mITT and EI populations is  $\leq 5\%$ , only the analyses based on the EI population will be provided.

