6.2. Subject Withdrawal

Subject eligibility must be confirmed at each visit by an appropriate member of the investigator's study team as described in Sections [4](#) and [5.9.2](#). If a subject is discontinued from vaccination and the subject consents, safety follow-up will be conducted for 1 month after the last dose of vaccine.

Subjects may withdraw from the study at any time at their own request, or they may be withdrawn at any time at the discretion of the investigator or sponsor for safety (see also the Withdrawal From the Study Due to Adverse Events section) or behavioral reasons, or the

inability of the subject to comply with the protocol-required schedule of study visits or procedures at a given study site.

If a subject does not return for a scheduled visit, every effort should be made to contact the subject. All attempts to contact the subject and information received during contact attempts must be documented in the subject's medical record. In any circumstance, every effort should be made to document subject outcome, if possible. The investigator should inquire about the reason for withdrawal, request that the subject return for a final visit, if applicable, and follow up with the subject regarding any unresolved AEs.

If the subject withdraws from the study, and also withdraws consent for disclosure of future information, no further evaluations should be performed, and no additional data should be collected. The sponsor may retain and continue to use any data collected before such withdrawal of consent.

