7.2. Immunogenicity Assessments

Serum samples will be obtained for immunogenicity testing at Visit 1 (Month 0, immediately before Dose 1) and Visit 5 (Month 7, 1 month after Dose 3).

Both toxin A- and toxin B-specific neutralizing antibody levels will be measured. Approximately 20 mL (minimum of 10 mL and up to 20 mL) of blood will be collected to allow for adequate volume required for repeat testing or additional antigen-specific immunogenicity testing to be performed.

Refer to the SRM for details regarding serum sample management and storage.

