9.2. Immunogenicity Analysis

The immunogenicity data will be summarized according to the vaccine group (active vaccine and placebo) as received in the evaluable immunogenicity population, and according to the vaccine group as randomized in the modified intent-to-treat (mITT) population. Subjects receiving vaccine who did not follow their randomization assignment will be excluded from the evaluable immunogenicity population.

The *C difficile* toxin A– and toxin B–specific neutralizing antibody levels at each blood sampling time point will be summarized by GMCs (any *C difficile* toxin A– or toxin B–specific neutralizing antibody level that is below the lower limit of quantitation [LLOQ] will be assigned as $0.5 \times \text{LLOQ}$) and the associated 95% confidence intervals (CIs). The GMC will be calculated as the mean of the assay results after making the logarithm transformation and then back transformation to its original scale. Two (2)-sided 95% CIs will be constructed by back transformation of the CI for the mean of the logarithmically transformed assay results computed based on the Student's t distribution.

Exact 2-sided 95% CIs will be compiled using the Clopper-Pearson method for any proportions of subjects with *C difficile* toxin A– or toxin B–specific neutralizing antibody level \geq cutoff (LLOQ).

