**Table 1. Summary of Major Changes in SAP Amendments**

SAP Version	Change	Rationale
1	Not Applicable	Not Applicable
2	[REDACTED]	[REDACTED]
3	Minor updates in Sections 3.4.3, 3.5.1, 3.5.3.1, 4.2, 4.3, 6.1.3, and 6.4.	
CCI
 
 
• Adverse events (AEs) will be summarized from day of first dose rather than from signing of the informed consent document (ICD).
 
• Analysis of AEs during the 30 minutes immediately after dosing was deleted because time-of-collection data are not available.
 
• Clarification was added to the duration calculations for reactogenicity events, based on FDA comments for the study data standardization plan.
 
• Immunogenicity analysis using the modified intent-to-treat (mITT) population will be limited based on the relative size of the mITT population.
 
• Clarifications on the populations for analysis of reactogenicity and AEs were added.
 

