### 6.4.2. Study Conduct and Subject Disposition

The numbers and percentages of subjects who signed the ICD, withdrew during the study period, and completed the study will be included in a disposition summary. The reasons for withdrawal will also be tabulated. The reasons for withdrawal will be those specified in the database; no rewording/recoding will be done.

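### Does the 5% size condition on the mITT immunogenicity analyses leave the lot-consistency result unchecked against exclusions that differ between lots?

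*SAP*

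**What the plan says.** SAP 4.1 makes EI the primary immunogenicity population: all three doses as randomized, Month 7 blood drawn 23 to 47 days after Visit 4, a valid result for either toxin, and no major protocol deviation. SAP 4.2 admits to mITT any randomized subject with at least one dose who "have at least 1 valid and determinate assay result for either toxin A or toxin B for the specified analysis". It then adds the condition: "Immunogenicity analyses using the mITT population will be conducted only if the mITT population size exceeds the size of the EI population by" more than 5%. At 5% or less, only EI results are reported.

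SAP Table 1 discloses this as a Version 3 change, saying that mITT immunogenicity analysis "will be limited based on the relative size of the mITT population". Protocol 9.2 plans the mITT summary, by group as randomized, with no size condition. Protocol 9 allows the SAP to modify protocol plans, provided that major changes to the primary endpoint or its analysis also go into a protocol amendment.

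SAP 4 has population membership settled "prior to unblinding and releasing the database, and classifications will be documented per standard operating procedures". On disposition, SAP 6.4.2 says "The reasons for withdrawal will also be tabulated" and names no grouping. SAP 5.1.1 rests the primary decision on EI: all six GMC-ratio confidence intervals must lie within (0.5, 2).

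**The concern.** The primary claim is equivalence between lots in a population that loses subjects after randomization. If exclusions fell more heavily on one lot, and the excluded subjects responded differently, the EI ratios for that lot would move. An mITT analysis is the usual way to see this. The condition compares only total sizes. Equal exclusions in every group can trigger the analysis with no imbalance at all, while a concentration in one lot can leave it switched off.

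The count is also underspecified. SAP 4.2 fixes EI size as the base in its first sentence, and the reference to the specified analysis partly anchors the time point. It does not say whether placebo is included, which toxin applies, or whether a baseline result alone qualifies a subject. Two programmers could disagree on whether the analysis runs. At stake is whether a lot-consistency conclusion could depend on exclusions that no reported table shows.

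**Working it through.** **Inputs.** Protocol 9.1 and SAP 2.2.2: SDs on the natural log scale 0.899 (toxin A) and 1.485 (toxin B), difference 0.2, 263 evaluable per lot, up to 20% nonevaluable, total 1316 (329 per group). Margin ln 2 = 0.693, two-sided 95% CI.

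**The plan's own figures.** For toxin B, SE = 1.485 × √(2/263) = 0.1295. Two one-sided t tests with a true difference of 0.2 give 96.72% power, and 0.9672³ = 90.5%, as in the plan's power table. 263/0.8 rounds up to 329, and 4 × 329 = 1316. The inputs reproduce.

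**How the condition behaves on one overall Month 7 count** (assumption: all 1316 have a Month 7 result).
- 62 excluded: 62/1254 = 4.94%, analysis not run, even if all 62 are in one lot.
- 16 excluded in each of the four groups: 64/1252 = 5.11%, analysis run with no imbalance.

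At the planned EI size (1052), the largest excess with no mITT analysis is 52 (52/1052 = 4.94%). If all 52 were in one lot, that would be 52/263 = 19.8% of its EI size. So the condition does not track imbalance between lots.

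**How the counting choice matters.**
- 15 excess in each lot and none in placebo: 45/1052 = 4.3% over four arms, 45/789 = 5.7% over the three lots.
- Baseline result sufficient, planned nonevaluable rate: 1316/1052 − 1 = 25%. The mITT analysis would run.

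**Size when the condition is not met.** Take the 62 exclusions as random over four equal groups (multinomial, 1,000,000 draws), with the excluded 1 SD lower on toxin B.
- The largest gap between lots has median 6: exp(6/329 × 1.485) = 1.03-fold.
- The gap is 13 or fewer in about 96% of draws: exp(13/329 × 1.485) = 1.06-fold.
- CI half-width at 329 against 329: t × 1.485 × √(2/329) = 0.227. With an observed EI difference of 0.2 and a gap of 13, the mITT upper limit is exp(0.2 + 0.0587 + 0.227) = 1.63, inside 2.
- Some lot holding 31 or more of the 62: at most 3 × P(Bin(62, 0.25) ≥ 31) = 5.9 × 10⁻⁵.

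**Extreme bound.** With all 62 in one lot, the mITT limit reaches 2 only if the excluded differ by (0.693 − 0.227 − 0.2)/(62/329) = 1.41 log units, a 4.1-fold lower GMC. If only 31 of them have a Month 7 result, the lot has n = 298 and half-width 0.233. The difference needed is then (0.693 − 0.233 − 0.2)/(31/298) = 2.50 log units, about 12-fold.

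**Would a within-lot 5% condition be better?** It would be met at 16 excluded in a lot (16/313 = 5.11%) and not at 15 (15/314 = 4.78%).
- It is met by 16 in every lot, with no imbalance.
- Under the random spread of 62, at least one lot reaches 16 in about 95% of draws.
- Exclusions of 15, 15 and 0 leave it unmet, although that gap exceeds the 13 that covers 96% of chance draws.

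**The case for a change.** The best case for a change is that it is cheap. Protocol 9.2 promised the mITT summary without a condition, and the only stated basis for limiting it is relative size. The visible text plans no table of EI exclusions by lot and reason. Stating the count, or dropping the condition and adding that table, would cost a sentence and one or two outputs, and would not touch alpha, sample size or the decision rule.

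Part of this stands. The count is incompletely described, and the condition is not a detector of lot imbalance. But it was never offered as one: its purpose is to skip a second set of tables when they would nearly repeat the first. The missing counting detail can be settled when populations are classified, before unblinding. An overall count needs no lot codes at that stage, whereas a within-lot count would.

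The added output would also tell less than it seems. Immunogenicity blood is drawn only twice: "Serum samples will be obtained for immunogenicity testing at Visit 1" and at Visit 5. For a subject discontinued from vaccination who consents, Protocol 6.2 promises that "safety follow-up will be conducted for 1 month after the last dose of vaccine", with no Month 7 immunogenicity sample assured, and mITT cannot recover a sample that was not taken. Grouping as randomized also brings back subjects whom Protocol 9.2 removes: "Subjects receiving vaccine who did not follow their randomization assignment will be excluded from the evaluable immunogenicity population". If 5% of one lot received the other lot, a true ratio of exp(0.2) = 1.221 becomes exp(0.19) = 1.209, slightly closer to 1, so agreement with EI would be only mildly reassuring.

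Text is blacked out beside the primary analysis and between SAP 6.1.3 and 6.4, so it cannot be shown that a by-lot exclusion table or further mITT analysis is absent.

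**Conclusion.** The observation about the wording is accurate, but no change to the plan follows. A sponsor who applies SAP 4.2 as written, on any reasonable count, reaches the same primary conclusion, because that conclusion rests on EI alone. If a baseline result qualifies a subject, the planned nonevaluable rate would trigger the mITT analysis anyway. If only Month 7 results count, the analysis is skipped only when the populations differ by 5% or less. There the expected effect on a toxin B lot ratio is about 1.03-fold, and at most 1.06-fold in about 96% of random draws, against a 2-fold margin.

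These sizes assume 329 per group with a Month 7 result, an SD of 1.485, excluded subjects 1 SD lower, and exclusion unrelated to lot. The last assumption is well supported: the lots look identical, site and laboratory staff are blinded, and populations are fixed before unblinding. The planned EI size gives a similar bound: holding the half-width at 0.254, all 52 excess subjects would have to be in one lot and differ by (0.693 − 0.254 − 0.2)/(52/315) = 1.45 log units. What remains is a detail that analysts can settle at classification, and supportive output that would not be expected to alter any result.
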